### 11.4 Data Analysis

A Statistical Analysis Plan (SAP) will be written and finalised prior to database lock and treatment unblinding. The SAP will give a more detailed description of the summaries and analyses that will be performed, expanding on the protocol specified analysis. Any deviation from the protocol specified analysis will be documented within a protocol amendment or in the SAP, as appropriate, and described within the CSR.

Data will be analysed using SAS® version 9.4 or a later version.

Continuous variables will be summarised using number of non-missing observations, mean, standard deviation, median, first and third quartiles, minimum and maximum values. Categorical variables will be summarised using counts and percentages. All statistical hypothesis tests and confidence intervals will be two sided, using a type I error rate of 0.05. No adjustment for multiple comparisons will be used for this Phase 2 study. For the analysis of each efficacy endpoint pairwise statistical comparisons are planned for each NT-814 dose group (40mg, 80mg, 120 mg and 160 mg) versus placebo, with the understanding that this increases the overall type I error rate of the study. All collected subject data will be listed.

No subgroup analyses are planned to be performed.

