### **2.2. Randomization Methodology**

Eligible subjects will be randomised on Day 1 to NT-814 or placebo. Randomisation will be performed centrally via an interactive web response system (IWRS) and is integrated into the Electronic Data Capture (EDC) system. The randomisation schedule (both the initial and any updates following IA) will be produced and entered into the IWRS by Pharm Olam International according to their Standard Operating Procedures.

An adaptive design will be used to maximise the efficiency of the study through discontinuation or reduction in the number of subjects randomised to doses that are found, on the basis of emerging data, to be either insufficiently effective or no more effective than an adjacent lower dose. Doses may also be discontinued for safety reasons and the randomisation ratio may be adjusted in favour of one or more doses without necessarily discontinuing other doses.

On successful completion of screening and confirmation of eligibility, subjects will initially be randomised in a 1:1:1:1:1 ratio to receive either NT-814 40 mg/day, 80 mg/day, 120 mg/day, 160 mg/day or placebo. Randomisation will be stratified by region (North America or Europe). After completion of the first interim review the randomisation ratio may be changed. Regardless of any changes to the randomisation ratio, subjects will continue to receive the dose regimen they were randomised to for the full 12-week treatment period.

The initial estimated sample size for the study is 165 subjects. However, the total number of subjects may be higher or lower according to the outcome of the interim analyses.

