## **4. STATISTICAL METHODS**

### **4.1. Sample Size Justification**

The total sample size for the trial yields high power for the expected large difference from placebo in hot flush reduction from baseline and adequate power for moderate difference.

Assuming a common standard deviation (SD) of 4.4, N=27 per treatment group has ~95% power ( $\alpha=0.05$  2-sided) via trend test across all doses including placebo if the true underlying dose response is non-decreasing from a reduction of 4 moderate or severe hot flushes per day on placebo up to 8 on the highest dose of NT-814. N=33 per treatment group is required for 95% power for pairwise comparison of the highest dose to placebo under these same assumptions. Hence, a total of 150 completed subjects (30 x 5) was used for the simulations of adaptive design. [Note, the actual performance / power for the adaptive designs may be higher than the values cited in this report since additional subjects will be added to selected dose groups to better inform on safety.] The actual sample size is determined by the adaptive dose-finding design algorithm (See Appendix B from the protocol). In addition, the actual sample size is increased by 10% to allow for subjects who withdraw prematurely and so the initial sample size is 165 subjects.

The interim reviews will also include a review of the estimates used in defining the starting sample size. If the observed variance or delta are lower than the original estimates the sample size for the dose groups that are continuing to be evaluated may be increased. For this reason, the protocol permits a total of up to 300 subjects to be randomised into the study.

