This method allows for a general unstructured variance-covariance matrix and will include data from subjects with incomplete data from some scheduled time points. The model will be implemented in SAS using the MIXED procedure and will include the change from baseline as the dependent variable. The fixed effects in the model will include independent variables of randomized treatment, visit (nominal post-baseline visits as per the schedule of assessments) and treatment-by-visit interaction, along with the following baseline covariates: Baseline frequency or severity, Region (section 4.2.3). Visits will be treated as a repeated variable within a patient. Patient, treatment and visit will be treated as factor variables. An unstructured variance-covariance structure will be applied to model the within-patient errors. The model will be fitted using the Restricted Maximum Likelihood (REML) method. Denominator degrees of

freedom will be estimated using Kenward-Roger's approximation.

Pairwise statistical comparisons are planned for each NT-814 dose group (40 mg, 80 mg, 120 mg and 160 mg) versus placebo. To estimate the difference between the treatment groups in mean change from baseline to Week 4 and Week 12, a treatment-by-visit interaction contrast will be constructed (i.e., the treatment group contrast at Week 4 and 12). On the basis on this analysis, least square means, standard errors, and the 95% confidence interval for the treatment difference (at Week 4 / 12, primary endpoint timepoints) will be reported.

SAS code:

```
PROC MIXED DATA= dataset;  
CLASS region avisitn treat subjid;  
MODEL chg=base treat region avisitn treat*avisitn / ddfm=KENWARDROGER;  
REPEATED avisitn / subject=subjid type=un;  
LSMEANS treat*avisitn / cl pdiff;  
ODS OUTPUT lsmeans=lsmeans_ tests3 = tests3_ diffs = diffs_  
convergenceStatus=convergenceStatus_  
WHERE avisitn > xx;  
RUN;  
* chg represents the mean change from baseline variable;  
* base represents the mean daily frequency (or severity) at baseline;  
* treat represents the treatment group;  
* avisitn represents the analysis visits as defined in section 4.2.12. Only the  
post-baseline visits must be included  
* region represents the categorical covariate related to stratification factors;  
Further options to control the output may be added.  
From ODS OUTPUT, using the correct visit/treatment selection, the outputs will  
allow getting the following:  

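### The co-primary MMRM has no baseline-by-visit term, so if the baseline slope differs between visits it loses a little precision and mis-adjusts chance baseline imbalance at Weeks 4 and 12

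*SAP*

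**What the plan says.** SAP 4.6.1 gives the mean model as "MODEL chg=base treat region avisitn treat*avisitn", with an unstructured covariance, REML and Kenward-Roger degrees of freedom. The text of that section agrees with the code. Treatment-by-visit is the only interaction named, and baseline frequency or severity and region are listed as covariates. SAP 4.2.3 adds no further term. Weeks 1, 2, 4, 8 and 12 enter the model.

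The same section plans an ANCOVA with treatment, baseline and region, fitted separately at Week 4 and Week 12, as a sensitivity analysis. SAP 7.1 lists its tables for frequency and severity on the FAS, PP set and mFAS.

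Protocol 11.9.1 asks only for a mixed model repeated measures analysis and leaves the mean model open.

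The planning figures are in SAP 4.1: "Assuming a common standard deviation (SD) of 4.4, N=27 per treatment group has ~95% power" for a dose response "non-decreasing from a reduction of 4 moderate or severe hot flushes per day on placebo up to 8 on the highest dose of NT-814". The documents give no baseline SD and no baseline slope at any visit.

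**The concern.** A daily flush count cannot fall below zero, so the possible reduction is capped by the baseline count. Entry needs an average of at least 7 moderate or severe flushes per day (Protocol 7.2). The earlier trial saw reductions of up to 9 from a baseline of about 10 to 12 (Protocol Appendix B), and the targets here are reductions of 6 and 8 (SAP 4.3.2). If reductions are roughly proportional to baseline, the slope of change on baseline follows the proportional reduction. That could be smaller at Week 1 than later, yet all five visits share one slope.

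At stake is how well the primary model adjusts for chance imbalance at Weeks 4 and 12, both co-primary. Randomisation is stratified by region only, and "subjects will initially be randomised in a 1:1:1:1:1 ratio" before any adaptation. Arms may later be small: Table 1a of Appendix B shows an average as low as 13.9 on one active dose against 28.8 on placebo. With an assumed baseline SD of 4, the SE of the baseline difference is 4 x sqrt(2/30) = 1.03 flushes/day at 30 per arm, and 4 x sqrt(1/13.9 + 1/28.8) = 1.31 in that case.

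**Working it through.** **The plan's own figure.** Inputs: two-sided 0.05 (Protocol 11.4: "All statistical hypothesis tests and confidence intervals will be two sided, using a type I error rate of 0.05"), SD 4.4, difference 8 - 4 = 4. The SAP states that "N=33 per treatment group is required for 95% power for pairwise comparison of the highest dose to placebo under these same assumptions". The noncentral t distribution gives 94.7% power at 32 per group and 95.3% at 33, so 33 is reproduced. Likewise 0.95^4 = 81.5% (Protocol 11.1.1 says about 81%), and 150 x 1.1 = 165. These calculations use the raw SD of change without baseline adjustment, so the stated sample size does not depend on the missing term.

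**Formulas.** Take complete data, residual covariance S and true visit slopes b. The fitted common slope tends to bc = (1'S^-1 b)/(1'S^-1 1). At visit t:
- error in the treatment effect, given a baseline difference D: (b_t - bc) x D;
- SE ratio, common slope over separate slopes: sqrt(1 + sx^2 (b_t - bc)^2 / s_t^2), where sx is the baseline SD and s_t^2 = (SD of change)^2 - b_t^2 sx^2.

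Because b_t is negative, a negative b_t - bc means under-correction and a positive one over-correction. If all slopes are equal, b_t - bc = 0 and the ratio is 1.

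**Inputs.** From the documents: SD of change 4.4, or about 4.4 at 4 weeks falling to about 3.6 at 12 weeks (Appendix B), and 30 per arm ("a total of 150 completed subjects (30 x 5) was used for the simulations of adaptive design"). Assumed: slopes -0.35, -0.45, -0.55, -0.65, -0.75 at the five visits; baseline SD 3, 4 or 5; SD of 4.0 at Week 8 in the falling case; residual correlation exchangeable 0.6 or AR(1) 0.8.

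**One setting in full** (SD 4.4, baseline SD 4, AR(1)). Here bc = -0.631.
- Week 12: s^2 = 19.36 - 0.5625 x 16 = 10.36; b_t - bc = -0.119; ratio = sqrt(1 + 16 x 0.119^2/10.36) = 1.011.
- Week 4: s^2 = 19.36 - 0.3025 x 16 = 14.52; b_t - bc = 0.081; ratio = sqrt(1 + 16 x 0.081^2/14.52) = 1.004.

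**All settings:**

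| SD of change | Baseline SD | Correlation | bc | Week 4 error per unit D | Week 4 SE ratio | Week 12 error per unit D | Week 12 SE ratio |
|---|---|---|---|---|---|---|---|
| 4.4 | 3 | exch. | -0.608 | 0.058 | 1.001 | -0.142 | 1.006 |
| 4.4 | 3 | AR(1) | -0.589 | 0.039 | 1.000 | -0.161 | 1.008 |
| 4.4 | 4 | exch. | -0.668 | 0.118 | 1.008 | -0.082 | 1.005 |
| 4.4 | 4 | AR(1) | -0.631 | 0.081 | 1.004 | -0.119 | 1.011 |
| 4.4 | 5 | exch. | -0.766 | 0.216 | 1.048 | 0.016 | 1.001 |
| 4.4 | 5 | AR(1) | -0.713 | 0.163 | 1.028 | -0.037 | 1.003 |
| 4.4 to 3.6 | 3 | exch. | -0.733 | 0.183 | 1.009 | -0.017 | 1.000 |
| 4.4 to 3.6 | 3 | AR(1) | -0.681 | 0.131 | 1.005 | -0.069 | 1.003 |
| 4.4 to 3.6 | 4 | exch. | -0.800 | 0.250 | 1.034 | 0.050 | 1.005 |
| 4.4 to 3.6 | 4 | AR(1) | -0.747 | 0.197 | 1.021 | -0.003 | 1.000 |

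Baseline SD 5 with a Week 12 SD of 3.6 is impossible, since 0.75 x 5 = 3.75 exceeds 3.6. Where bc is steeper than every true slope (for example -0.800), the generalised least squares weights on some visits are negative. That is how Week 12 can be over-corrected. Week 4 is over-corrected throughout because I assumed that slopes steepen steadily.

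**In flushes.** For a one-SE imbalance at 30 per arm (0.77, 1.03 and 1.29 for baseline SD 3, 4 and 5), the largest errors are 0.161 x 0.77 = 0.12 at Week 12 and 0.216 x 1.29 = 0.28 at Week 4, against a planned difference of 4.

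**Wider assumptions.** I also let slopes run from constant (-0.50) to as far apart as -0.20 and -0.75, with exchangeable correlation 0.7 or AR(1) 0.8. The Week 12 SE ratio was 1.000 to 1.037 and the model made 72% to 118% of the right Week 12 correction. The Week 4 SE ratio reached 1.13. Errors per unit imbalance reached 0.21 at Week 12 and 0.39 at Week 4. The Week 12 power gained by adding the term was at most 0.3 points for a difference of 4 and 0.9 points for a difference of 3. In simulation (baseline SD 4, AR(1) 0.8, 3000 runs per pattern) the common-slope estimate was unbiased over randomisations in all four slope patterns. Dropout and the severity endpoints were not simulated.

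**The case against.** The strongest reply is that the premise is not demonstrated and the plan already contains a check. No visit-specific slope is reported. Protocol 5.2 says that another NK3 antagonist reached its maximum improvement within 2 weeks, which argues against a steady steepening to Week 12. The ANCOVA gives each co-primary week its own slope, so a slope-driven discrepancy would show. The planned model is valid and contradicts nothing in the protocol.

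Most of this stands, and it is why the point is conditional and small. It does not remove the point. Early onset would still leave Week 1 sharing a slope with later visits. The ANCOVA uses only subjects observed at the visit, so if it disagreed with the MMRM, slope handling and missing data could not be told apart.

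Two stronger readings are tempting. A reader might infer that the model over-corrects early and under-corrects late, so that Week 12 is biased. The documents do not support this: under the plan's own SDs the Week 12 error runs from -0.16 to +0.05 per unit of imbalance, and it is an error conditional on the observed imbalance, not bias over randomisation. A reader might also put the Week 12 variance loss at about 5%, which a residual SD of 3.8 with baseline SD 5 and slope -0.75 produces. But that implies an SD of change of sqrt(3.8^2 + 0.75^2 x 25) = 5.34, well above the plan's 4.4.

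Finally, the floor argument concerns counts. It does not carry over by itself to severity or the questionnaire scores.

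**Conclusion.** The structural point is certain: code and text impose one baseline slope on five visits. The consequence depends on the slopes differing, which is an inference. If they differ as assumed, the cost is a Week 12 SE up to about 1% larger and a Week 4 SE up to about 5% larger (about 4% and 13% under the wider assumptions), plus a conditional error up to about 0.16 and 0.25 flushes/day respectively per 1 flush/day of imbalance. Week 4 can be affected more than Week 12, and the direction at Week 12 is not fixed. If the slopes are equal, nothing is lost.

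This is an optional refinement. It does not threaten the validity of the primary analysis, and neither the stated sample size nor the planned power is affected in any way that matters. The figures rest on assumed slopes, baseline SDs and correlations, complete data and 30 per arm, and apply to frequency only.

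**What to change.** Add `base*avisitn` to the MODEL statement of the co-primary MMRM in SAP 4.6.1 and name the interaction in the accompanying text and in SAP 4.2.3. For consistency, do the same in the secondary MMRMs of SAP 4.6.2 that reuse the model; no separate gain has been shown for those or for severity. Make the change before unblinding.

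The cost is one term and about 4 degrees of freedom. The LSMEANS statement and the ANCOVA stay as they are. Since Protocol 11.9.1 does not fix the mean model and Protocol 11.4 leaves analysis detail to the SAP, no protocol amendment appears to be needed.

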#### 4.6.2. Secondary analysis

##### 4.6.2.1. Other hot flush frequency and severity secondary endpoints

The following hot flush frequency and severity secondary endpoints will be summarised by treatment group and scheduled visit (as applicable). In addition, the same approach as for the primary endpoint (MMRM incorporating post-randomization data collected up to treatment discontinuation at week 12) will be used to provide estimates of the change from baseline to weeks 4 and 12.

- Mean change from baseline in mean daily frequency of moderate and severe hot flushes from baseline to Weeks 1, 2, 8 and 16
- Mean change from baseline in mean weekly severity of moderate and severe hot flushes from baseline to Weeks 1, 2, 8 and 16
- Mean change from baseline in mean daily frequency of all hot flushes from baseline to Weeks 1, 2, 4, 8, 12 and 16
- Mean change from baseline in mean weekly severity of all hot flushes from baseline to Weeks 1, 2, 4, 8, 12 and 16
- Mean change from baseline in the mean daily Hot Flush Score (frequency x severity) at Weeks 1, 2, 4, 8, 12 and 16

The above endpoints will be derived using the 7 last days with at least one available data in the evening and/or the morning before the corresponding visit using the same method described in

section 4.2.11. For Week 1, the first 7 post-baseline days with at least one available data in the evening and/or the morning will be used.

The mean change from baseline and the corresponding 95% CI will be displayed graphically by visit on the observed values and by treatment groups.

The proportion of responders, defined as a reduction from baseline of  $\geq 50\%$  and  $\geq 80\%$  on the average mean daily frequency of moderate and severe hot flushes by week will be summarised at each evaluation time.

The proportion of responders will be calculated using the percent change from baseline as below at a visit Week x:

$$\text{Percent change} = (\text{change from baseline in mean daily frequency of moderate and severe HF from baseline to Week } x / \text{Mean daily frequency of moderate and severe HF at baseline}) * 100$$

A subject will be considered as responder with reduction of  $\geq 50\%$  (or  $\geq 80\%$ ) if the percent change is  $\leq -50$  (or  $\leq -80$ ).

The Week 4 and Week 12 response will be analysed using a logistic regression. The model will be implemented in SAS using the LOGISTIC procedure and will include the responder variables as response variable. The fixed effects in the model will include independent variable of randomized treatment, along with the following baseline covariates: Baseline frequency of moderate and severe HF, Region.

The odds ratio will be used as a measure of association between treatment and response and will be calculated such that an odds ratio  $>1$  is favourable for NT-814. The 95% confidence interval for the odds ratio assumes asymptotic normality of the Wald estimate for the regression coefficient. The Wald p-value associated to the treatment covariate in the logistic regression will be provided. In addition, as a sensitivity analysis, the adjusted relative risk of response will be calculated from a Cochran-Mantel-Haenszel test adjusted on the categorized randomization stratification factor: Region (North America/Europe).

SAS code:

```
PROC LOGISTIC DATA= dataset;
CLASS treat (ref='Placebo') region / param=ref;
MODEL response (event='1') = base treat region;
ODS OUTPUT OddsRatios=OddsRatios_ ParameterEstimates=ParameterEstimates_;
RUN;
* base represents the baseline value of the endpoint;
* response represents the response variable;
* treat represents the treatment group;
* region represents the categorical covariate related to stratification factors;
Further options to control the output may be added.
From ODS OUTPUT, using the correct selection, the outputs will allow getting the
following:
- OddsRatios_: Odd ratio and 95% CI for each treatment
- ParameterEstimates_: p value.

PROC FREQ DATA = dataset;
Tables region*treat*response / cmh;
```

CONFIDENTIAL

```
WHERE treat in ("Placebo","NT-814 40mg");  
RUN;  
* The p-value would be for "Row Mean Scores Differ" in the SAS PROC FREQ output.
```

The following night time awakenings secondary endpoints will be summarised by treatment group and scheduled visit (as applicable). In addition, the same approach as for the primary endpoint (MMRM incorporating post-randomization data collected up to treatment discontinuation at week 12) will be used to provide estimates of the change from baseline to weeks 4 and 12.

- Mean change from baseline in mean daily number of night time awakenings secondary to hot flush at Weeks 1, 2, 4, 8, 12 and 16
- Mean change from baseline in mean daily number of all night time awakenings at Weeks 1, 2, 4, 8, 12 and 16

The above endpoints will be derived using the 7 last days with at least one available data in the morning before the corresponding visit using the same method than the one described in section 4.2.8.

Night time awakenings secondary to hot flush correspond to severe hot flash recorded on the morning diary, and all night time awakenings correspond to the data recorded in "Total number of times you woke up last night?" field from eDiary recorded in the morning. Number of NTAs secondary to HF can't be higher than number of all NTAs.

The mean change from baseline and the corresponding 95% CI will be displayed graphically by visit on the observed values and by treatment groups.

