It is hypothesised that in the menopausal state the KNDy neurons are in a state of hyperactivation (consistent with the observed hypertrophy) which could disrupt baseline thermoregulation and trigger hot flushes. Therefore, modulation of the KNDy neurons could be a viable therapeutic approach to controlling hot flushes. Clinical evidence supporting the hypothesis comes from a study in healthy women in which it was shown that intravenous infusion of NKB (endogenous ligand that binds the NK3 receptor) acutely induces hot flushes in healthy women. Furthermore, two recently completed proof of concept studies with NK3 receptor antagonists have provided direct evidence that NK3 receptor blockade can reduce the number and severity of hot flushes. In a 12-week study in post-menopausal women, twice daily dosing with the NK3 antagonist fezolinetant resulted in a sustained reduction in the frequency (-93% vs -54% for placebo) and severity (-70% vs -23%) of hot flushes (HF). The maximum improvements were apparent within 2 weeks of the start of treatment. In a 4-week study with the NK3 antagonist MLE4901, the reduction in HF frequency was 78.4% compared to a reduction of 45.6% with placebo.

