## **11.9.2 Secondary Efficacy Analysis**

### **11.9.2.1 Other hot flush frequency and severity secondary endpoints**

Each of the hot flush frequency and severity secondary endpoints, including night time awakening (Section 8.2), will be summarised by treatment group and scheduled visit (as applicable) and will be analysed, following the same approach as for the primary endpoint.

The proportion of responders, defined as a reduction of  $\geq 50\%$  points and  $\geq 80\%$  points on the weekly average frequency of hot flushes will be summarised at each scheduled visit. The Week 4 and Week 12 response will be analysed by logistic regression, including the same terms in the model as for the primary efficacy endpoint analysis. Pairwise statistical comparisons are planned for each NT-814 dose group versus placebo, presenting the adjusted odds ratio for the treatment difference with its corresponding 95% Wald confidence interval.

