### 11.9.2.2 Other Secondary endpoints

The analyses of the following endpoints will use the same approach as for the primary endpoint: Pittsburgh Sleep Quality Index scores, Insomnia Severity Index Scores, Beck Depression Inventory Scores, MenQoL and HFRDIS (total score and domain/sub-scores, as applicable).

For each of these secondary endpoints the appropriate analysis method to be used to assess the observed data will be reviewed, and any changes documented in the SAP. Only the Week 4 and Week 12 time points will be analysed, other visits summarised only, by treatment group.

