#### 4.6.1. Co-primary analysis

The co-primary endpoints are the change from baseline in the mean daily frequency and mean weekly severity of moderate and severe hot flushes at Weeks 4 and 12.

For each timepoint (Baseline, Week 1, Week 2, Week 4, Week 8, Week 12) summaries will be produced which use data from the 7 days with at least one available eDiary data entry in the evening and/or the morning before the Visit date:

- These 7 days do not need to be consecutive.
- As the data entered in the morning diary is assigned to the previous calendar day (a diary day comprises an evening and a morning entry, in that order) the morning diary with the same calendar date as the Visit day may be included in the calculation.
- For Week 1, the first 7 post-baseline days with at least one available data in the evening and/or the morning will be used.

The methods for calculating the endpoint are the same as described in section 4.2.11.

Absolute and changes from baseline in the mean daily frequencies and mean weekly severity of moderate and severe hot flushes will be summarised by treatment group. Percent changes from baseline in the mean daily frequencies will be also summarised.

The change from baseline will be calculated as follow:

Mean daily frequency (or mean severity) at week 4 (or Week 12) – Mean daily frequency (or mean severity) at baseline.

The percent change from baseline will be calculated as follow:

(Change from baseline / Mean daily frequency at baseline) \* 100.

The mean change from baseline and the corresponding 95% confidence interval (CI) will be displayed graphically by visit on the observed values and by treatment groups.

Bar graphs of the change from baseline at Week 4 and Week 12 will be produced for each treatment group.

The change from baseline endpoint will be analysed using a Mixed-Effect Model Repeated Measures (MMRM) incorporating post-randomization data collected up to treatment discontinuation at weeks 12 (Week 1, 2, 4, 8 and 12 will be included; Week 16 visit data will not be included in the model) and with consideration of the variance-covariance matrix of the repeated measures.

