## **5. CHANGES TO PLANNED ANALYSES**

As of this date, there have been no changes between the protocol-defined statistical analyses and those presented in this statistical plan.

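### SAP 4.6.2.1 reports diary secondary endpoints against placebo only at Weeks 4 and 12, leaving 28 of 38 named endpoint-weeks with no prespecified reported estimate and no declared change

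*SAP*

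**What the plan says.** SAP 4.6.2.1 lists five hot-flush endpoints and states that the co-primary MMRM "will be used to provide estimates of the change from baseline to weeks 4 and 12". The first endpoint under that sentence is "Mean change from baseline in mean daily frequency of moderate and severe hot flushes from baseline to Weeks 1, 2, 8 and 16". The second is its severity counterpart, at the same four weeks. The other three (frequency of all flushes, severity of all flushes, hot flush score) are named at Weeks 1, 2, 4, 8, 12 and 16. The two awakening endpoints follow the same Week 4 and 12 sentence, for example "Mean change from baseline in mean daily number of night time awakenings secondary to hot flush at Weeks 1, 2, 4, 8, 12 and 16".

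SAP 4.6.1 fits the model to Weeks 1, 2, 4, 8 and 12, adds that "Week 16 visit data will not be included in the model", and names Weeks 4 and 12 as the time points for which the treatment difference is reported.

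Protocol 11.9.2.1 says the hot-flush and awakening secondary endpoints "will be analysed, following the same approach as for the primary endpoint" and sets no limit on weeks. The limit is in Protocol 11.9.2.2, which covers the sleep, insomnia, depression, quality-of-life and interference questionnaires: "Only the Week 4 and Week 12 time points will be analysed, other visits summarised only, by treatment group". Protocol 11.4 plans pairwise comparisons with placebo for every efficacy endpoint. SAP 4.2.1 promises formal tests of the secondary as well as the primary endpoints. SAP section 5 states that "there have been no changes between the protocol-defined statistical analyses and those presented in this statistical plan".

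**The concern.** For the first two endpoints, the stated estimates at Weeks 4 and 12 are the co-primary results again, and none of the weeks that define those endpoints is reported against placebo. For the other five, four of six named weeks are left out. The restriction that the protocol places on questionnaires appears in the SAP for diary endpoints, and nothing records this as a change.

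Two things are at stake. Named secondary endpoints would reach the study report without an adjusted difference from placebo. And if the team decided after unblinding to show the early or intermediate weeks, it would be choosing which weeks to show, although the model already contains them. The early weeks are of interest: for one 12-week study of another NK3 antagonist, Protocol 5.2 reports that "The maximum improvements were apparent within 2 weeks of the start of treatment".

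**Working it through.** **Count of named endpoint-weeks** (SAP 2.5.1.2 and 4.6.2.1)

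| Endpoints | Number | Named weeks each | Endpoint-weeks | Covered by Weeks 4/12 |
|---|---|---|---|---|
| Frequency and severity, moderate and severe | 2 | 4 (1, 2, 8, 16) | 8 | 0 |
| Frequency and severity of all flushes; score | 3 | 6 | 18 | 6 |
| Awakenings due to flush; all awakenings | 2 | 6 | 12 | 4 |
| Total | 7 | | 38 | 10 |

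- Not covered: 38 − 10 = 28, which is 7 endpoints × 4 weeks (1, 2, 8, 16).
- Dose-versus-placebo contrasts: 28 × 4 doses = 112, out of 38 × 4 = 152.
- Weeks 1, 2 and 8: 7 × 3 × 4 = 84. These visits are in the MMRM, and LSMEANS treat*avisitn with the pdiff option yields their differences, CIs and p-values.
- Week 16: 7 × 1 × 4 = 28. These are outside the MMRM.

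**Does another analysis fill the gap?** The Wilcoxon test, the ANCOVA and the ad hoc Emax and trend analyses in SAP 4.6.1 are all set at Weeks 4 and 12. None gives a between-group result at Week 1, 2, 8 or 16.

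**Is Week 1 a defined model level?** SAP 4.6.1 describes visit as the nominal visits in the schedule of assessments, which has no Week 1 visit. The code note sends avisitn to SAP 4.2.12, but that section excludes diary data and its Table 2 has no Week 1 row. The Week 1 averaging days are defined in SAP 4.6.1 (first 7 post-baseline days with data). The visit level is not.

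**Would a contrast be informative?** The point disputes no figure in the plan, but the planning inputs show what one contrast is worth.

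- Check of the plan's own figure (SAP 4.1: difference 4, SD 4.4, two-sided 0.05, 95% power): n = 2 × (1.960 + 1.645)² × 4.4² / 4² = 31.4, so 32 by the normal formula. With the t distribution, power is 94.7% at 32 and 95.3% at 33, so the stated 33 reproduces.
- 95% CI half-width at 30 per group: 1.96 × 4.4 × √(2/30) = 2.23 flushes per day. Over the SD range of about 3.4 to 4.9 that Protocol Appendix B gives for the two-week study, it runs from 1.96 × 3.4 × √(2/30) = 1.72 to 1.96 × 4.9 × √(2/30) = 2.48.
- Power at SD 4.4 and 30 per group: 93–94% for a difference of 4, 74–75% for 3, and 41–42% for 2.

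**The case against.** The strongest reply is that Weeks 1, 2 and 8 are already analysed. They are in the model, the code computes their contrasts, SAP 4.2.1 covers secondary endpoints, and the MMRM table titles in SAP 7.1 name no weeks. This stands as to computation: a reader who inferred that no treatment comparison exists at these weeks would be wrong. It does not settle reporting, because the text names Weeks 4 and 12 and the code notes take output after a visit selection.

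A second reply is that following the primary approach may include the primary's weeks, with detail left to the SAP. That is arguable for the five endpoints that include Weeks 4 and 12. For the two that do not, it leaves the endpoint with no analysis of its own.

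Third, a reader might infer that onset and offset of effect cannot be assessed at all. The documents do not support this. Every endpoint is summarised by arm and visit, mean change with 95% CI is plotted by visit and arm, and onset and offset are not objectives in Protocol 6.1 or 6.2. Nor does the protocol say that the diary runs to Week 16 to study loss of effect. The two-week peak comes from one study; Protocol 8.6.1 speaks more loosely of weeks for NK antagonists.

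Fourth, leaving Week 16 out is coherent with a model restricted to data up to treatment discontinuation. A Week 16 comparison could also be affected by restarted medication: Protocol 8.6.6 allows some restarts at Week 12. The documents conflict on hormonal therapies, which Protocol 9.8 bars throughout the study while the Appendix A heading ends the bar one week after the last dose. Those passages must be reconciled. This stands, and it makes a descriptive Week 16 defensible if the plan says so.

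**Conclusion.** The point holds as a conflict in prespecified reporting. Of 38 named endpoint-weeks, 28 (112 of 152 contrasts) have no dose-versus-placebo estimate selected for reporting. For 84 contrasts the estimate exists in the specified model and only the reporting rule omits it; 28, all at Week 16, have no model. The restriction departs from Protocol 11.9.2.1 and 11.4 and from SAP 4.2.1, and is not declared in SAP section 5.

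The time course can be described, but has no prespecified adjusted between-group estimate outside Weeks 4 and 12. The co-primary analyses are unaffected. The responder endpoint is not part of the gap, since it is named at Week 12 and analysed there, so it would be wrong to say that every hot-flush secondary endpoint is affected.

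The counts assume that all four doses are compared with placebo at the end. The precision figures assume 30 per group and the planning SD at every week; adaptive allocation and covariate adjustment will change them.

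**What to change.** - In SAP 4.6.2.1, state that for the seven diary endpoints the treatment-by-visit contrasts versus placebo, with 95% CIs, are reported at Weeks 1, 2, 4, 8 and 12 from the existing MMRM.
- Define the Week 1 level of avisitn for diary data, and stop pointing to SAP 4.2.12 for it.
- For Week 16, choose one and write it down: either declare it descriptive only and record that in SAP section 5, or add an exploratory ANCOVA of the form already coded in SAP 4.6.1, labelled off-treatment and with the caveat that restarted medications may affect it.
- Keep the Week 4 and 12 limit for the questionnaires.

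The cost is extra rows in existing MMRM tables and, if the ANCOVA is chosen, one table per diary endpoint. The 84 added contrasts would give 84 × 0.05 = 4.2 expected false positives if every null hypothesis were true (112 × 0.05 = 5.6 with Week 16), so they should be read as unadjusted. Protocol 11.4 already accepts unadjusted comparisons in this Phase 2 study.
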